10.1.	INFORMED CONSENT.....	27
10.2.	CONFIDENTIALITY.....	27
11.	PUBLICATION OF RESEARCH FINDINGS.....	27
12.	PROTOCOL SIGNATURE PAGE.....	28
12.1.	PRINCIPAL INVESTIGATOR.....	28
12.2.	UNIT DIRECTOR OR UNIT PHYSICIAN.....	28
12.3.	UNIT NURSE DIRECTOR.....	28
13.	REFERENCES.....	29

ANNEXES I-III

LIST OF ABBREVIATIONS USED IN THIS PROTOCOL

AHC	Alcohol-based handrub consumption
ABHR	Alcohol-based handrub
CI	Contact isolation
cRCT	Cluster-randomized controlled study
ESBL	Extended-spectrum beta-lactamase
ESBL-E	Extended-spectrum beta-lactamase producing Enterobacteriaceae
FTE	Full-time-equivalent
GEE	Generalized Estimating Equation
HCW	Health care worker
HH	Hand hygiene
HICPAC	Healthcare Infection Control Practices Advisory Committee
IC	Infection control
LOS	Length of stay
MDR-GNB	Multi-drug resistant Gram-negative bacteria
MDRO	Multi-drug resistant organism
SP	Standard precautions
WP	Work Package

1. SYNOPSIS

Title of the Protocol	Patient isolation strategies for extended-spectrum beta-lactamase producing Enterobacteriaceae (ESBL-E)-carriers in medical and surgical hospital wards
Protocol chair	[name]
Intervention	
The study will compare 2 Non-ICU-level infection control strategies designed to reduce transmission of ESBL-E among patients in adult medical and surgical wards with universal admission and discharge screening.
 
The 2 strategies are as follows:

Standard Precautions (SP)	
 • Hand hygiene (HH) • Use of gloves and other barriers as needed for interactions involving contact with mucous membranes, wounds, and body fluids by healthcare workers (HCWs) during the care of all patients
Contact Isolation (CI)	
 • HH and standard precautions for all patients AND • Use of gloves and gowns during the care of all patients known to be colonized/infected with ESBL-E prior to admission or who are identified as such during their stay on the ward. These patients should be cared for preferably in a single room or in a shared room with patients colonized or infected with the same organism.
Objectives	
Primary Objective	To determine the additional effects of CI compared to a SP strategy on the incidence density of ESBL-E-acquisition among hospitalized patients in adult Non-ICU wards in hospitals with universal ESBL-E admission and discharge screening.
Secondary Objectives	
 • To determine the prevalence of ESBL-E carriage on admission • To determine the incidence of nosocomial ESBL-E infections in the study periods • To evaluate compliance with hand hygiene in the study intervention periods • To evaluate compliance with contact precautions in the study intervention periods • To compare ESBL-E-incidence detected with and without universal surveillance screening (study intervention periods vs. baseline period and post intervention period)

Hypotheses/Outcome	
Primary Hypothesis and Outcome	If all ESBL-E-carriers are identified through universal surveillance screening, Contact Isolation (CI) will not reduce incidence densities of ESBL-E-acquisition among patients in medical and surgical wards when compared to SP. The primary outcome is the ESBL-E acquisition rate per 1,000 patient days. Acquisition of ESBL-E-carriage is defined as recovery of ESBL-E isolates from clinical and/or rectal/perianal/stool screening specimens >3 days after admission (admission day = day 1) from patients with negative admission screening results. If a patient is discharged from the ward and re-admitted to the ward on the same or the following day, then the discharge will be ignored in the primary analysis. If the readmission occurs later, the patient will be treated as a new case.
Secondary Hypotheses	
 1. Healthcare workers (HCWs) will not practice HH more frequently during contact with known ESBL-E-carriers in CI than in SP 2. HCWs will practice HH more frequently during contact with known ESBL-E-carriers than with patients not known to be ESBL-E-carriers
Secondary Outcomes	The trial will assess the efficacy of the CI strategy in reducing the incidence density of colonization with ESBL-E by the methods described above. In addition, the trial will evaluate the efficacy of the CI strategy in reducing the cumulative incidence of ESBL-E infections as determined by laboratory-based surveillance of clinical culture results. The trial will evaluate the frequency of hand hygiene and the use of gloves and gowns by HCWs, as assessed by bedside observations of a trained monitor. The antibiotic use will be analysed for all patients in defined daily doses (DDD) preferably weekly/at least monthly. In a subset of ESBL-E-patients antibiotic use will also be analysed at patient level in days of therapy (DOT). The trial will evaluate the consumption of alcohol-based handrub (ABHR) per patient days to evaluate differences between ESBL-E-carriers and Non-ESBL-E-patients as well as differences between the two IC strategies. Because the interventions involve minimal risk, no specific safety measures will be made.
Study Design	The study is a two-arm, cluster-(Non-ICU) randomized, controlled study (cRCT) of two IC strategies with cross-over design, which will be performed in different European countries. Randomization will be performed at the ward level. Primary analyses will be performed at the ward level.

Study population	
Inclusion criteria	
 • Adult medical and surgical Non-ICUs with approval from the medical director and head nurses, approximately 1000 admissions/year and an expected non-varying average length of stay for the 2 intervention periods • Ability to implement a universal ESBL-E admission and discharge screening • Written approval of the study from the local Institutional Review Board (IRB)
Exclusion criteria	
 • Transplant and paediatric wards, ICUs • Wards planning to enrol subjects in a study of an investigational agent administered for the purpose of eradicating or preventing colonization with ESBL-E or to reduce the likelihood of transmission of these bacteria
Sample Size	
Assuming an average new acquisition of ESBL-producers in hospital of 0.8/100 patients on non-ICUs, a design effect (DE) of 2.9 and a corresponding intracluster correlation coefficient (ICC) of 0.003, 20 wards with 36.788 included patients (18.394 per study arm) will have the a power of at least 80% to detect at least a 50% reduction in risk in wards during CI vs. SP period with a Type I error rate of 0.05 for a 2-sided test.

Randomization	
Randomization will occur at the ward level with a block size of 2. Groups of two consecutive wards will be randomized to one of the two arms.

Data Analyses	
For the primary efficacy analysis, incidence density of nosocomial ESBL-E acquisition will be computed at hospital level and ward level. A one degree of freedom test from an analysis of multivariate model will be used to test for differences in mean incidence density ratios of ESBL-E acquisition between the two strategies. This will be calculated by Poisson or negative-binomial regression analysis with monthly aggregated data using Generalized Estimating Equation (GEE) models with adjustment by several confounding parameters besides cluster effects by ward and hospital.

2. PERSONS / INSTITUTIONS INVOLVED IN THE STUDY

2.1. SPONSOR

R-GNOSIS is an EU-funded research project funded by the Seventh Framework Programme (FP7) under the grant agreement number 282512.

3. BACKGROUND

Approximately 30 % of all healthcare-associated infections are caused by *Enterobacteriaceae*. The rapidly increasing prevalence of extended-spectrum beta-lactamase producers among common *Enterobacteriaceae* species (ESBL-E) in Europe is a cause for concern^{1, 2}.

“To isolate or not to isolate” patients with ESBL-E is currently one of the most controversial questions in the field of infection control (IC). Most national guidelines recommend CI (CI) of patients with MRSA (methicillin-resistant *Staphylococcus aureus*) or VRE (vancomycin-resistant enterococci). For ESBL-E, the evidence is less conclusive^{3, 4} and is not investigated in wards with endemic ESBL-E levels but instead is often only derived from outbreak investigations. A recently published systematic review to examine the efficacy of IC interventions for the control of ESBL-E in hospital in non-outbreak settings identified only four uncontrolled retrospective studies⁵.

Consequently, only few national guidelines recommend isolating patients with ESBL-E on general hospital wards. The German guidelines for management of patients with multidrug resistant Gram-negative organisms⁶ do not recommend isolation of ESBL-E-patients in non-high risk wards. The 2006 US HICPAC guideline for “Management of multi-drug resistant organisms in healthcare settings” recommends CI, which includes physical separation of colonized patients in single rooms and wearing gloves and gowns by the HCWs⁷. If this is impossible, HCWs should, at least, wear gloves and gowns, but again, there is no convincing scientific evidence supporting this recommendation.

Moreover, isolation measures may be associated with increased costs and side effects for the individual patient such as depression and reduced contact with attending physicians^{8, 9, 10, 11}. The importance of the environment as an intermediary in the transmission of multidrug resistant organisms (MDRO) is also poorly understood¹². As *Enterobacteriaceae* generally lose viability quickly and are recovered less frequently from hospital environments than Gram-positive organisms, isolation in single rooms may not be required¹³. However, a recent study found substantial contamination of gloves and gowns with multidrug-resistant bacteria, thus supporting the use of gloves and gowns for treating these patients^{14, 15, 16}.

Standard precautions (SP) may be as effective for limiting the spread of ESBL-E, especially when hand hygiene compliance is high¹⁷, and one study even found lower hand hygiene compliance under isolation conditions¹⁸.

Currently, many hospitals in Europe are unable to isolate patients with MDRO due to shortage of single rooms, while, the prevalence of intestinal ESBL-E-carriage among healthy people^{19, 20},²¹ and people admitted to the hospital^{22, 23} has risen sharply to 3-7 % depending on the setting and the population studied. Moreover, if ESBL-E-carriers are identified solely by cultures

obtained for clinical purposes, many asymptomatic patients colonized with ESBL-E will remain undetected and thus will not be cared for with contact precautions.

Hence, a combined approach of active surveillance screening at admission and CI of detected ESBL-E-carriers would be the logical consequence. However, this would increase the management costs for ESBL-E-patients even further.

Implementing HICPAC guideline recommendations would have considerable cost implications and impact on the quality of patient care²⁴. Therefore, adding contact precautions for the rapidly increasing number of patients colonized with ESBL-E should be based on solid evidence.

Last but not least, transmission prevention should not be considered an end in itself but rather one particular strategy to achieve the higher goal of reducing clinical infections and associated morbidity and mortality¹². This should also be investigated before final conclusions about isolation strategies for ESBL-E-patients are made.

4. OBJECTIVES AND HYPOTHESES

4.1. OBJECTIVES

4.1.1. PRIMARY OBJECTIVE

- To determine the additional effects of CI compared to a SP strategy on the incidence density of nosocomial ESBL-E-acquisition among hospitalized patients in adult Non-ICU wards in hospitals with universal ESBL-E admission and discharge screening

4.1.2. SECONDARY OBJECTIVES

- To determine the prevalence of ESBL-E-carriage on admission
- To determine the incidence of nosocomial ESBL-E infections in the study periods
- To evaluate the compliance with hand hygiene in the study intervention periods
- To evaluate the compliance with contact precautions in the study intervention periods
- To compare ESBL-E-incidence detected with and without universal surveillance screening (study intervention periods vs. baseline period and post intervention period)

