5.1. STUDY DESIGN

The study is a two-arm, cluster-randomized, controlled study (cRCT) of two IC strategies with cross-over design, which will be performed in 4 European countries to achieve high external validity of study results.

An attempt will be made to identify all intestinal ESBL-E-carriers by active surveillance testing and cultures obtained for clinical indications.

Two IC strategies (CI and SP) will be compared for ESBL-E-positive patients in different units for 12 months each. Because these IC strategies will be implemented as a unit-wide measure, all patients hospitalized in a specific unit will be subjected to the allocated IC strategy of the unit (figure 1). Wards will be assigned to the IC strategy in a random order and will then switch strategies after a wash-out period of one month in the following year.

Figure 1: Study design WP5

The two strategies are as follows:

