5.2. STANDARD PRECAUTIONS (SP) (= CONTROL ARM)

For all patients – including known ESBL-E-carriers – SP will be performed. The indications and technique for HH will be consistent with those recommended by the WHO’s “Five Moments”²⁵. Clean gloves and gowns/aprons will be used for all interactions that involve potentially infectious procedures⁷. Non-sterile gloves are considered adequate; non-latex-gloves are used for medical staff and/or patients with latex allergy. Gloves should be changed after contact with

infectious material, such as blood, stool, urine or wound drainage. Gloves should be removed immediately after use and HH should be practiced before touching non-contaminated surfaces or going to another patient. Accordingly, clean gowns/aprons should be donned if contact with patient's blood or body fluids is expected. Gowns should be removed promptly after use and HH should be practiced before touching non-contaminated surfaces or going to another patient. This strategy represents the current standard of care and all patients will be subjected to this IC strategy on wards in the SP phase of the trial.

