5.3. CONTACT ISOLATION (CI) (= INTERVENTION ARM)

All patients who are known to be colonized/infected with ESBL-E prior to admission or as a consequence of the surveillance cultures and/or of cultures obtained for clinical indications will be cared for using contact precautions, preferably in a single room or in a shared room with patients who are colonized with the same organism. If isolation in a single room or a shared room with patients colonized with the same organism is impossible, gloves and gowns/aprons will be used for all interactions with the patient or the patient's environment in a shared room. Clean gloves and gowns/aprons will be used for all interactions that involve direct contact with the patient or the patient's environment⁷. Non-sterile gloves are considered adequate; non-latex-gloves are used for medical staff and/or patients with latex allergy. Gloves should be changed after contact with infectious material, such as blood, stool, urine or wound drainage. Gloves should be removed immediately after use and hand hygiene should be practiced before touching non-contaminated surfaces or going to another patient. Clean gowns/aprons should be donned if contact with the patient or with environmental surfaces in the patient's room is expected. Gowns should be removed promptly after use and HH should be practiced before touching non-contaminated surfaces or going to another patient. HH will be performed according to WHO's "Five Moments"²⁵. As the intervention strategy will be implemented as a unit-wide IC measure, all patients known to be colonized/infected with ESBL-E-producing bacteria will be subjected to this IC strategy on wards in the CI phase of the trial.

Both strategies (SP and CI) will be applied in all units for a period of 12 months each with a washout period of one month between the 2 study periods.

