5.7. STUDY PERIODS AND TIMELINE

The study will be divided into a three-month baseline period, a first 12-month intervention phase, a one-month washout period, a second 12-month intervention phase and a three-month post intervention period.

During the baseline and the post-intervention period, only data on nosocomial ESBL-E-acquisition detected by clinical sampling will be collected on the participating wards. In the intervention phases, data on ESBL-E-acquisition detected by active surveillance testing as well as clinical sampling will be collected.

During the one-month washout period, the protocol of the following intervention period will be applied. Only data on nosocomial ESBL-E-acquisition detected by clinical sampling will be collected except for the Follow-up of patients admitted during the preceding period.

Figure 2: Timeline WP5 for Participating Wards

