9.2.3. ANALYSES OF PRIMARY OUTCOMES

The incidence density of ESBL-E-acquisitions in the SP strategy and the CI strategy will be compared in total and at study arm, hospital level and ward level.

In the univariate and multivariable analysis, crude and adjusted incidence-density ratios of ESBL-E-acquisition between the two strategies will be calculated by Poisson or negative-binomial regression analysis with, at best, weekly (if this is impossible at least monthly) aggregated data using Generalized Estimating Equation (GEE) models. Additionally, a Generalized Linear Mixed Model (GLMM) will be used to consider temporary trends in the periods. In total, 480 observation months will be analysed for the 20 wards with 12 observation months each per IC strategy. To analyse 1 degree of freedom in the regression model (e.g. a dichotomous parameter or a continuous parameter), 20 observations are required. The log number of patient days will be treated as offset parameter.

The models will take into account for the clustering effects "hospital" and "ward" and will consider the following parameters: strategy, type and size of ward, type and size of hospital, antibiotic use of different antibiotic groups (DDD/1000 patient days or PDD/100 patients), staff equipment and the burden of ESBL-E at admission (ESBL-E patients on admission per 100 admitted patients), after grouping wards into "higher" or "lower" ESBL-E burden based on median proportion of ESBL-E carriers on admission.

A GLMM model with parameters not on the causal pathway between exposure and outcome and based on expert knowledge and will be considered (i.e. strategy, antibiotic use, staff equipment, burden of ESBL-E on admission, time trend). Parameters with a causal connection

to nosocomial ESBL-E-acquisitions such as AHC and single room use will not be considered in this model.

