9.2.4. ANALYSES OF SECONDARY OUTCOMES

The incidence density of hospital-acquired infections caused by ESBL-E in the CI period with the SP period will be compared in total and ward levels. Additionally, a regression model will be performed to adjust by confounders.

The incidence density of clinical isolates with ESBL-E will be analysed by segmented regression using 31 observation months (3 month baseline, 12 month first intervention, 1 month washing out, 12 month second intervention, 3 month post intervention). Incidences of the different study phases will also be compared and tested.

To analyse the difference in HH practice for known ESBL-E patients in the two intervention periods, AHC will be calculated for ESBL-E-positive patient days (per ESBL-E-positive patient day) in both intervention periods at total and ward levels and differences will be tested.

To analyse the differences in the HH practice between known ESBL-E-carriers (use in ESBL-E-positive patient days) and patients not known to be ESBL-E-carriers (use in ESBL-E-negative patient days), AHC consumption in ESBL-E-positive and -negative patient days will be calculated separately at total and ward levels and by intervention period and differences will be tested.

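### The comparison with and without universal screening pools CI and SP months, so about half of any CI effect would be mixed into it

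*Protocol*

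**What the plan says.** The secondary objective in section 4.1.2, repeated in the synopsis, is: "To compare ESBL-E-incidence detected with and without universal surveillance screening (study intervention periods vs. baseline period and post intervention period". It treats the intervention periods as one block.

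That block holds two strategies. Section 5.3 states: "Both strategies (SP and CI) will be applied in all units for a period of 12 months each". Section 5.1 adds: "Wards will be assigned to the IC strategy in a random order".

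Section 9.2.4 plans a segmented regression of clinical ESBL-E isolates "using 31 observation months (3 month baseline, 12 month first intervention, 1 month washing out, 12 month second intervention, 3 month post intervention". It then says that incidences in the study phases will be compared and tested. Strategy is listed as a model parameter for the primary outcome in 9.2.3, but not for this regression.

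On the unscreened periods, section 5.7 says: "During the baseline and the post-intervention period, only data on nosocomial ESBL-E-acquisition detected by clinical sampling will be collected". Isolation practice in those months is not stated. The nearest statement is in 5.2, on SP: "This strategy represents the current standard of care".

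**The concern.** If wards work under SP before and after the intervention periods, two things differ between the compared periods. Universal screening is added, and in half of the ward-months known carriers are also isolated. The objective attributes the contrast to screening alone.

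The calendar segments do not separate the two. Because the order is randomised, the first and the second intervention phase each contain some wards in CI and some in SP. Longer baseline periods would not help either, since the mixing comes from how the contrast is defined.

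At stake is the reading of one secondary objective. A fall in clinical isolates produced by isolation could be read as following from screening, or the gain in detection from screening could look smaller than it is. The background section treats screening combined with isolation as a package with cost implications, so it is useful to be able to tell the two apart.

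**Working it through.** **Inputs from the protocol**
- 20 wards (5.8, 9.1); months per ward 3, 12, 1, 12, 3 (9.2.4).
- 12 months of each strategy in every ward (5.3), in random order (5.1).
- Powered effect of CI: a 50% reduction (9.1), that is, a CI/SP ratio r = 0.5.

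**Assumptions**
- Equal patient-days under CI and SP.
- SP practice in the baseline and post-intervention periods.
- For the illustration, no true effect of screening (s = 1).

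**Step 1: the plan's own counts.** 3 + 12 + 1 + 12 + 3 = 31 months. 20 × 12 × 2 = 480 ward-months, which agrees with 9.2.3: "480 observation months will be analysed for the 20 wards with 12 observation months each per IC strategy". Of these, 20 × 12 = 240 are CI and 240 are SP, so the CI share is 240/480 = 0.5. Baseline and post-intervention supply 20 × 3 = 60 ward-months each.

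**Step 2: does the calendar split help?** If order is balanced, as the block size of 2 in the synopsis suggests, 10 wards are in CI in each intervention phase. Each phase then has 10 × 12 = 120 CI and 120 SP ward-months, the same 50:50 mix as the pooled block.

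**Step 3: size of the mixing.** Pooled ratio = s × (0.5 + 0.5 × r). With s = 1:

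| CI/SP ratio r | Pooled ratio | SP months only |
|---|---|---|
| 1.0 | 1.00 | 1.00 |
| 0.9 | 0.95 | 1.00 |
| 0.8 | 0.90 | 1.00 |
| 0.7 | 0.85 | 1.00 |
| 0.5 | 0.75 | 1.00 |

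At the powered effect, the apparent fall is 25%, half of the 50% CI effect.

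**Step 4: if CI can prevent only some isolates.** Section 9.2.4 models clinical isolates. Let p be the share of them that CI could act on. No document gives p, so the values here are illustrative. Pooled ratio = 1 − p × (1 − r)/2. With r = 0.5, p = 0.5 gives 0.875 and p = 0.25 gives 0.9375, apparent falls of about 13% and 6%.

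**Step 5: if the contrast is about detection.** Suppose screening truly raises detected incidence five-fold (an illustrative figure). At r = 0.5 the pooled contrast would show 5 × 0.75 = 3.75-fold.

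**The case against.** **The objective speaks of detected incidence.** It does not claim a causal effect of screening on transmission, and the change in ascertainment between periods is probably the larger difference. This stands for the total count, where a gain of 3.75-fold instead of five-fold leaves the qualitative message intact. It has less force for 9.2.4. Clinical isolates are counted in every period, so the ascertainment change does not hide a CI effect there to the same degree.

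**A strategy term may sit in a statistical analysis plan not shown.** That is possible, and the absence of a term alone would not be a finding. But the protocol itself fixes the contrast and the segments, and these create the mixing. An analysis restricted to SP months would depart from 4.1.2 as written.

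**Study phases in 9.2.4 may mean the SP and CI phases.** Sections 5.2 and 5.3 do use the word that way. In 9.2.4, however, it follows directly on a list of calendar segments, so the meaning is at best ambiguous.

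**Practice outside the intervention periods is unknown.** This stands. If some wards then isolated clinically detected carriers, the figures above change. The SP-only contrast would also be confounded, because isolation would be withdrawn as screening began.

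**The effect may be nil.** Under the primary hypothesis in 4.2.1, that CI does not reduce acquisition, pooling does no harm. That is correct, but it is what the trial sets out to test, so a secondary contrast should not depend on it.

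**Conclusion.** The point holds as a limited flaw in one secondary comparison. As written, the contrast between periods with and without screening takes in about half of any CI effect. The pooled ratio is 0.95 to 0.75 for CI/SP ratios of 0.9 to 0.5, given no screening effect, equal patient-days and SP practice outside the intervention periods. The 25% apparent fall is an upper illustration at the powered effect. The ratio is nearer 1 if only some clinical isolates are preventable, and 1.00 if CI does nothing.

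A reader might infer that the whole effect of isolation is credited to screening. The documents do not support that: only the 50:50 average enters. Nor do they show that the trial will report a causal screening effect, since the objective is worded as detection. A reader might also think that new data are needed on isolation outside the intervention periods. The ward-data table in 6.2 already lists a daily count of patients isolated for ESBL-E, and the restriction to intervention periods is attached to a different row.

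The CI versus SP comparison, the primary analysis and the sample size are not affected.

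**What to change.** 1. In 4.1.2, the synopsis and 9.2.4, fit the 31-month analysis on ward-level series with a strategy term (CI yes/no), so that the screening coefficient refers to SP. Alternatively, report SP months and CI months separately against baseline and post-intervention. Keep the pooled comparison as description only.
2. Say how the washout month is coded. Section 5.7 applies the protocol of the following phase in that month, so the strategy indicator should match.
3. State the isolation practice in the baseline and post-intervention periods, and report the daily ESBL-E isolation count from 6.2 for those months. The SP-only contrast is clean only if practice then was SP.

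**Cost.** This is wording and one model term; strategy is known by design for every ward-month. Reporting SP months alone uses 12 instead of 24 screened months per ward, while the version with a strategy term keeps all 24. For item 3, it is enough to confirm that the count in 6.2 is collected in all periods.
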